3.C.6.b. Specific Aim 1: Outcome Analyses. The primary outcome is 7-day ppa at 6-months.¹⁴⁴ The primary study analyses will adopt an intent-to-treat (ITT) strategy; secondary complete-case, as-treated analyses, and analyses that evaluate the role of treatment intensity (i.e., "dose") will also be conducted. In ITT analyses, the association between treatment group and 7-day ppa at 6-months will be evaluated using a logistic regression model that will have abstinence as the binary outcome, treatment groups as the main predictor, and covariates identified in preliminary bivariate analyses. Subjects who fail to return for the 6-month visit, decline ECO testing, or have discrepant abstinence and ECO results (that cannot be clarified with saliva cotinine strips) will be considered non-abstinent. This is a standard primary outcome when measuring the efficacy of a smoking cessation intervention in a definitive trial.^{21,144} It will be defined as a negative response to the validated question *Have you smoked cigarettes (even a puff) in the last 7 days, including today?*⁹¹ combined with an ECO level <10 ppm (or negative salivary cotinine when applicable).²³ Additional measures of abstinence or tobacco usage reduction will be similarly examined for association with treatment group in secondary analyses.⁹¹ Abstinence data will be collected at 1 and 3 months to assess the correlation between time points. [[A formal cost-effectiveness analysis that includes detailed accounting of effects on health-care utilization over time is beyond the scope of the project. However, we will calculate incremental cost per quit using our abstinence data and the economic metrics listed in 3.C.5. This is a standard cost-effectiveness metric for tobacco treatments,¹⁴⁵ and it will be calculated with bootstrap 95% confidence intervals to provide a starting point for discussions about the cost-economics of tobacco treatment in this population. This outcome is bound to overestimate the ultimate cost of a widely-disseminated intervention, because web-based programs of this sort are scalable at low expense.]]

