[[3.C.6.e. Sample Size Considerations: Aim 1. Using the mean abstinence rates in the SC arms in our two recent R21 trials (9.7%²¹ and 4.3%¹⁴), and up-adjusting the rate slightly in consideration of the attention-placebo, we estimate a 7-day ppa at 6 months in the control condition will be 7.5%. Our estimate of the efficacy of PSFW+ is based on research by our team²⁰ and others⁶² who have demonstrated that visits to an online community increase abstinence rates. In the BecomeAnEX outcome evaluation,²⁰ 7-day ppa at 6 months ranged from 11.1% (ITT) to 20.7% (responder only); individuals who visited the online community two or more times were more than twice as likely to be abstinent than those who never visited (OR=2.22, 95% CI 1.34-3.69, P=.002) controlling for a broad range of demographic, smoking, and psychosocial covariates. These results are consistent with An et al.⁶² who reported a near doubling of abstinence rates (OR=1.91) among individuals who used individual messaging in an online cessation program. The benefits of an online community are not simply for the minority who actively post; reading communications ("lurking") also has beneficial effects.^{150,151} Therefore, we estimate that PSFW+ combined with our intensive adherence strategies to promote engagement and utilization will increase abstinence rates by 2.05 times over control, yielding a 6-month quit rate of 15.4%. This estimate is deliberately conservative in that we have chosen to use as the base rate our estimate of control (7.5%) rather than the quit rate from our previous trial of PSFW (10.1%). This will ensure that we are adequately powered to detect treatment group differences between PSFW+ and control. Assuming abstinence rates of 15.4% and 7.5% in the PSFW+ and control conditions, respectively, 254 subjects in each arm will be necessary to achieve power of 0.8 with an alpha=0.05. Projecting a liberal 9.2% loss-to-follow-up based on our previous NIH-funded trials (R21CA163100-01, R21DA023362), we will randomize N=275 per arm.]]

Sample Size Considerations: Aim 2. We are able to detect a mediation effect (coefficient product) of small size

(with coefficient product parameters $a=0.14$, $b=0.14$) with at least 80% power for each mediator given our expected sample size of $N=508$ at 6 months.¹⁵²

3.C.7. Potential Problems and Solutions

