1) successful recruitment of overall sample size and racial/ethnic minorities in accordance with targeted enrollment projections, and 2) study completion rate of $\geq 90\%$. In the unlikely scenario that recruitment lags, research staff will recruit in clinics and extend recruitment until recruitment goals are met. MMC and MGUH both enjoy collegial academic relationships with nearby HIV-care centers caring for thousands of additional PLWH smokers, and these may serve as secondary referral sources if the need to augment recruitment arises. If follow-up rates are <90%, we will implement more intensive follow-up strategies and increase incentives as our budget permits.

Year 1				Year 2				Year 3				Year 4				Year 5													
Q1 Q2 Q3 Q4				Q1 Q2 Q3 Q4				Q1 Q2 Q3 Q4				Q1 Q2 Q3 Q4				Q1 Q2 Q3 Q4													
Website Development																													
		RCT Recruitment (14.5 subj/month * 38 months; N=550)																											
				Follow-up assessments (N=550)																									
Manuscript preparation																													

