1. Describe rates of and duration of tobacco abstinence, and identify clinical and demographic factors associated with maintenance of abstinence, among participants of the parent study.
2. Identify associations between smoking status and COVID-19 related outcomes and healthcare utilization among participants of the parent study.
3. Identify associations between smoking status on HIV-related outcomes and healthcare utilization among participants of the parent study.

Methods

This will be a prospective study of participants in the trial: *Randomized Controlled Trial of An Internet Cessation Program Plus Online Social Network for HIV + Smokers*. The trial was conducted at two sites, Montefiore Medical Center and Johns Hopkins University Hospital. Only the participants from the Montefiore site will be invited to join the follow-up study proposed in this amendment. For the sake of the amendment, “participants” refers to participants at Montefiore. All prior participants in the study are eligible for this proposed follow-up study. Study personnel will contact prior participants via telephone to offer participation in the follow-up study.

The first component of the follow-up study will include a 15-20 minute IRB-approved telephone interview with questions related to: current smoking status; smoking quit attempts; motivation to quit; alcohol and drug use; COVID-19 illness, management, vaccination status, and attitudes toward vaccination; overall healthcare utilization over the prior year including visits with an HIV provider, emergency department visits, and hospitalizations; and questions related to perceptions of HIV care.

Participants who report tobacco abstinence during the telephone interview will be invited for an in-person visit to measure exhaled carbon monoxide and to submit a cheek swab for biobanking for future genetic research. Both of these are painless, essentially risk-free procedures.

Data Security:

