Data will be collected and stored using a secure, password protected database accessible only to authorized study personnel. Data will be de-identified and all participants will be assigned a unique identifier. A file linking identifying information to unique identifiers will be kept separately from the data itself and will be stored in a locked file cabinet within a locked office, only accessible to authorized study personnel. Upon completion of the analysis, the documents linking the identifiable data to unique study identifiers will be destroyed.

Data Analysis:

Participants achieving tobacco abstinence will be compared to those not achieving abstinence according to clinical characteristics, sociodemographic characteristics, and interview responses. Using standard bivariate and multivariate methods, we will identify factors associated with tobacco abstinence, healthcare utilization, COVID-19 related outcomes and interview responses, and HIV-related outcomes and interview responses.

Informed Consent

All participants will undergo the process of informed consent prior to enrollment in this follow- up study. For participants in the telephone interview component, verbal informed consent using an IRB-approved script will be obtained. For participants in the in-person visit component, signed informed consent using an IRB-approved document will be obtained. Participants agreeing to the cheek swab for biobanking of genetic material for future research will also provide signed informed consent for that specific procedure.

Reimbursement:

Participants who consent to and complete the telephone interview will be reimbursed \$20 for their time. Participants completing the in-person study visit will be reimbursed an additional \$50. Participants participating in the in-person study visit will also be reimbursed for a \$6 Metrocard for roundtrip travel to the study site.

Risks/Benefits/Alternatives:

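### The follow-up amendment seeks factors associated with maintaining abstinence, but its stated comparison estimates factors associated with being abstinent

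*Combined protocol and SAP*

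**What the plan says.** All but the last two items come from the amendment dated 10-4-21.

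- **Objectives, item 1.** Besides describing rates and duration of abstinence, the study is to "identify clinical and demographic factors associated with maintenance of abstinence, among participants of the parent study".
- **Methods, eligibility.** Only Montefiore participants are invited, and among them "All prior participants in the study are eligible for this proposed follow-up study". Smoking status at the end of the trial is not a condition.
- **Methods, interview.** The smoking and substance-use topics listed are "current smoking status; smoking quit attempts; motivation to quit; alcohol and drug use". No quit date, duration or relapse item is named.
- **Data Analysis.** "Participants achieving tobacco abstinence will be compared to those not achieving abstinence". Then, by standard bivariate and multivariate methods, "we will identify factors associated with tobacco abstinence, healthcare utilization, COVID-19 related outcomes and interview responses". Maintenance is not mentioned here, and neither it nor *achieving* is defined anywhere in the amendment.
- **Protocol 3.C.6.b.** "The primary outcome is 7-day ppa at 6-months", confirmed by exhaled carbon monoxide or, where applicable, salivary cotinine. The trial therefore already holds a verified status from which maintenance could be measured.
- **Protocol 3.C.8, timeline table.** "RCT Recruitment (14.5 subj/month * 38 months; N=550".

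**The concern.** A person can maintain abstinence only after reaching it. A study of maintenance therefore needs a group known to be abstinent at some starting point, and compares those who stayed abstinent with those who relapsed. The stated comparison has no starting point.

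If *achieving* means abstinent at the telephone call, a participant abstinent since the trial and one who quit last month are the same success. A relapsed 6-month abstainer and a participant who never quit are the same failure. If *achieving* means abstinent during the trial, the comparison is about initial quitting. Neither reading estimates maintenance.

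A real predictor of staying abstinent could be missed, and a predictor of quitting could be taken for one. Time since randomisation adds to this. Planned recruitment ran for 38 months (38 / 12 = about 3.2 years), so exposure to both relapse and late quitting could differ by up to about 3 years between participants. The amendment does not say whether this enters any model.

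**Working it through.** The amendment states no sample size, power or effect size, so there is no figure to reproduce. The check is an illustration of what the two-group comparison would contain.

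**Inputs from the documents**
- Design rates (protocol 3.C.6.e): "Assuming abstinence rates of 15.4% and 7.5% in the PSFW+ and control conditions, respectively". With 1:1 allocation the mean is (15.4 + 7.5) / 2 = 11.45%.
- Planned Montefiore accrual (3.C.4.c): 6 to 7 a month for 38 months, so 6 × 38 = 228 to 7 × 38 = 266.

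These are planning figures, not results. The amendment names a different second site from the protocol, so the planned split between sites may not have held.

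**Assumptions, not in the documents**
- m = proportion of 6-month abstainers still abstinent at the call.
- l = proportion of the others abstinent at the call.
- Main grid: m = 40% to 80%, l = 5% to 15%.
- Favourable case: m = 70% and 1% a year quitting for 2 years, so l = 1 − 0.99² = 1.99%.

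**Step 1: who could maintain.** 228 × 0.1145 = 26.1 and 266 × 0.1145 = 30.5. About 26 to 30 people were abstinent at 6 months, before non-response to the call.

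**Step 2: make-up of the two groups.** The sample size cancels.
- Later-quitter share of the abstinent group = 0.8855 l / (0.1145 m + 0.8855 l).
- Relapser share of the non-abstinent group = 0.1145(1 − m) / [0.1145(1 − m) + 0.8855(1 − l)].

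| m | l | Later quitters among abstinent | Relapsers among non-abstinent |
|---|---|---|---|
| 70% | 1.99% | 0.0176 / 0.0978 = 18% | 3.8% |
| 80% | 5% | 0.0443 / 0.1359 = 33% | 2.7% |
| 60% | 10% | 0.0886 / 0.1573 = 56% | 5.4% |
| 40% | 15% | 0.1328 / 0.1786 = 74% | 8.4% |

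The comparator is the more lopsided group. Relapsers, who are the right comparison for maintainers, are about 3% to 8% of it throughout.

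**Step 3: a factor that affects maintenance only.** Take 50% prevalence and a true odds ratio of 2 for maintenance. At m = 60% the maintenance probabilities are 0.682 with the factor and 0.518 without (mean 0.60, odds ratio 2). With l = 10%:
- with the factor: 0.1145 × 0.682 + 0.08855 = 0.1667
- without: 0.1145 × 0.518 + 0.08855 = 0.1478
- observed odds ratio: (0.1667 / 0.8333) / (0.1478 / 0.8522) = 1.15

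Over the main grid it is 1.07 to 1.26. In the favourable case it is 1.21, so few later quitters does not remove the dilution.

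**Step 4: a factor that affects quitting by 6 months only.** Take 50% prevalence, an odds ratio of 2 for 6-month abstinence and none for maintenance. The 6-month probabilities are 0.1487 and 0.0803 (mean 0.1145). With m = 60%, l = 10%:
- with the factor: 0.1487 × 0.6 + 0.8513 × 0.1 = 0.1743
- without: 0.0803 × 0.6 + 0.9197 × 0.1 = 0.1402
- observed odds ratio: (0.1743 / 0.8257) / (0.1402 / 0.8598) = 1.30

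Over the main grid it is 1.12 to 1.55. In the favourable case it is 1.71.

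A factor irrelevant to maintenance can therefore show a larger association than one that doubles its odds.

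**The case against.** The best defence is that the amendment is brief rather than wrong. It leaves *achieving*, *maintenance* and the model covariates undefined. Objective 1 pairs maintenance with duration, and the interview covers quit attempts. A duration-based definition that includes later quitters would fit the text. The Background section presents the cohort as a source of predictors of long-term cessation, and someone who quit after month 6 and stayed quit is a long-term success.

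Much of this stands, and it rules out several stronger statements that a reader might infer:

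- *That the 6-month status and time since randomisation are excluded from the analysis.* The text is silent on both.
- *That maintenance is the stated reason for using this cohort.* The stated reason is long-term cessation.
- *That results would be reported under the wrong name.* The Data Analysis section itself speaks of factors associated with tobacco abstinence.
- *That the study cannot meet Objective 1.* Only the comparison as written cannot. The verified 6-month status is held, and the full questionnaire may ask more than the listed topics.
- *That later quitters would be the majority.* This depends wholly on assumed rates.

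The defence does not supply an analysis of maintenance. No duration threshold, time-based model or restricted group is given, and the comparison misses the objective under either reading of *achieving*.

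**Conclusion.** The concern holds as a mismatch between Objective 1 and its analysis. That conclusion comes from the text and needs no assumed rate.

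The size is uncertain. The 18% to 74% range for later quitters and the diluted odds ratios rest on the design quit rates and on assumed retention and late-quit rates, so they show that the mixing could be material, not how large it will be. The figure of 26 to 30 possible maintainers rests on design rates and planned accrual, and non-response would lower it.

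This is a point to correct in a single-site observational add-on. It does not touch the randomised comparison or the trial's primary result. Objectives 2 and 3 are framed by smoking status and do not depend on it.

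**What to change.** Define maintenance in the amendment and link the interview data to the verified 6-month status. Then:

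1. **Maintenance.** Among participants verified abstinent at 6 months, compare those still abstinent at the call with those who relapsed. Two point-prevalence readings do not prove continuous abstinence, so use quit-date, duration and relapse answers to keep a relapse followed by a re-quit out of the maintained group. Confirm that the interview asks for these, and add them if not. Report descriptively if the count is too small for a model.
2. **Later quitting.** Among participants not abstinent at 6 months, compare those abstinent at the call with those still smoking, as a separate analysis.
3. **Time since randomisation.** Account for it in any model fitted.
4. **Pooled comparison.** Keep it if wanted, labelled as current abstinence.

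The cost is amendment wording, possibly a few interview items, and linkage to data already held. The linkage should be settled before analysis ends, because the Data Security section has the identifier link destroyed at that point. The downside is that the maintenance analysis will visibly rest on about 30 people or fewer and may support only description. The pooled comparison hides that limit but does not remove it.
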